### 7.6. Sample size

The best available evidence of the effect of kcal labelling on kcal ordered at restaurants is the meta-analysis of Crockett et al. 2018. The authors analysed the effects of 3 RCTs testing energy labelling in restaurants [21]. They demonstrated a statistically significant reduction of 47 kcal in energy purchased when menus were labelled. The weighted average kcal ordered in the no label condition was 706 kcal. These results suggest that we could expect a 7% energy reduction in the labelling condition compare to the control condition. Previous studies examining the effect of an increased availability of lower-energy products on food selection tend to produce similar or larger effects than kcal labelling tends to [39], [40].-In a previous trial we ran at virtual fast food restaurants ([osf.io/ajcr6](https://osf.io/ajcr6)), we found a between-subject variance of 47,224 for kcal ordered ( $SD = 217.3$ ).

In a two-level mixed model, including 6 observations per participant at level 1 and estimating a level 1 and level 2 variance of 47,244 for energy of the main, a sample size of 1,000 participants with  $\alpha = 0.05$  allows to detect 2% energy reduction and above at power = 0.93 due to labelling and/or availability, an additional 2% energy reduction (or above) in participants of higher educational qualification at power = 0.81 due to an interaction between labelling and highest educational qualification and/or an interaction between availability and highest educational qualification, an additional 2% energy reduction (or above) for unfamiliar menus at power = 0.86 due to an interaction between labelling and familiarity and/or an interaction between availability and familiarity (MLPowSim) [41].

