### 3. EXPERIMENTAL DESIGN

Participants will be enrolled in an online survey and make hypothetical menu choices. Participants will be randomized into a mixed-design experiment with 2x2 between-subjects conditions with factors of kcal labelling (absent vs. present) and availability (baseline availability of main dishes with  $\leq 600$ kcals vs. higher availability of main dishes with  $\leq 600$ kcals) and 6 repeated measures (3 familiar and 3 unfamiliar menus).

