### 7.2. Variables description

#### Primary outcome

The main outcome variable is the **energy of the main** selected in each dining out scenario in kcal.

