## 9. APPENDIX A: PROCESS OF ORDERING MAINS ITEMS ON THE MENUS

For the all conditions, the lowest calorie and highest calorie item were identified. Meanwhile, the remaining eight items were categorised as either 'higher' or 'lower' calorie items, making sure that there were four items in each of these categories. Below is the example of this for the American C/CL condition.

Classic Broccoli Blackened Shrimp Alfredo	1360 kcal	Highest
Riblet Platter	1290 kcal	Higher
Brunch Burger	1220 kcal	Higher
Double Crunch Shrimp	1170 kcal	Higher
Clubhouse Grille	1040 kcal	Higher
Grilled Chicken Caesar Salad	970 kcal	Lower
Classic Bacon Cheeseburger	870 kcal	Lower
Chicken Wonton Stir Fry	790 kcal	Lower
Signature Bourbon Street Steak	650 kcal	Lower
Cedar Salmon with Maple Mustard Glaze	370 kcal	Lowest

It was agreed that it is important that the lowest and highest calorie option are featured in certain positions on the menu. For example, it is important that the highest calorie option is featured at the 'top' of the menu as well as the 'bottom' and also being featured in the 'middle' of the menu. It is also important that the lowest calorie option is also featured on the menu in the same positions. Below is a table outlining what we mean by 'top' 'middle' and 'bottom' of the menu.

Position 1	Top
Position 2	Top
Position 3	Middle
Position 4	Middle
Position 5	Middle
Position 6	Middle
Position 7	Middle
Position 8	Middle
Position 9	Bottom
Position 10	Bottom

Below are six menu scenarios where you can see how these categories have formed different menu listings.

	1	2	3	4	5	6
Top	Highest Lower	Lower Highest	Lowest Higher	Higher Lowest	Lower Higher	Higher Lower

Middle	Higher Lower Higher Lowest Higher Lower	Lower Higher Lower Higher Lower Higher	Lower Higher Lower Highest Lower Higher	Higher Lower Higher Lower Higher Lower	Lower Higher Lowest Higher Lower Higher	Higher Lower Highest Lower Higher Lower
Bottom	Higher Lower	Lowest Higher	Lower Higher	Highest Lower	Lower Highest	Higher Lowest

It was also agreed that when 'highest' or 'lowest' items were featured in either the 'top' or 'bottom' positions, they should be counterbalanced by the opposite pair. For example, when the 'highest' item is at the top, this should be matched with a 'lower' item also being featured in the top section. Similarly, if the 'lowest' item was at the top, this should be matched with a 'higher' item also at the top.

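### Section 7.6 uses one between-subject variance from another task at both levels of the power model, leaving the within-participant variance, the ICC of 0.50 and the powers 0.93 / 0.81 / 0.86 unsupported

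*Combined protocol and SAP*

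**What the plan says.** Section 7.6 (Sample size) has one source of variability, the sponsor's own earlier work: "In a previous trial we ran at virtual fast food restaurants", where "we found a between-subject variance of 47,224 for kcal ordered" (SD 217.3).

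The next paragraph sets up a two-level model "including 6 observations per participant at level 1", "estimating a level 1 and level 2 variance of 47,244 for energy of the main". With "a sample size of 1,000 participants" and alpha 0.05 it claims power of:
- 0.93 for a 2% reduction from labelling or availability;
- 0.81 for a further 2% in the higher-education group;
- 0.86 for a further 2% on unfamiliar menus.

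The endpoint in Section 7.2 is the energy of the main dish "selected in each dining out scenario in kcal". Section 3 describes "6 repeated measures (3 familiar and 3 unfamiliar menus", so familiarity varies within participant.

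No within-participant variance, ICC or sensitivity range is given anywhere. The plan does not say which mean the 2% refers to. The change from 47,224 to 47,244 is a digit slip with no effect (SD 217.3 against 217.4).

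**The concern.** Three steps in the variance input have no stated support.

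1. **Endpoint.** A figure for kcal ordered in a fast-food task is carried over to main-dish energy on six restaurant menus, with no statement that the two are comparable.
2. **Level.** A between-subject variance does not tell us how much one person's choices differ across six cuisines.
3. **Double use.** Equal components force the ICC to 0.50. If the earlier figure was the variance of a single order per person, it already contains both components.

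The split matters because the tests draw on different components. Under a random-intercept model the familiarity interactions depend on level-1 variance alone. The main effects and education interactions depend mostly on level 2.

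The labelling-by-familiarity hypothesis is a stated secondary objective (Section 2). The familiarity interactions also decide whether the main analysis is stratified (Section 7.4) and how choices are averaged for the mediation analysis (Section 7.5). The stated power is therefore relied on beyond one test.

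**Working it through.** **Inputs.** From the plan: N = 1,000, six choices each (3 familiar, 3 unfamiliar), equal allocation (Section 6), alpha 0.05, and a lower-education share of 10% + 30% = 40% (Section 4.1 with the cut in Section 7.2).

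Assumed: two-sided tests, normal approximation, random participant intercept. The reference mean for the 2% is also assumed, in two versions:
- 706 kcal, the no-label average in Section 7.6: 0.02 × 706 = 14.12 kcal;
- 973 kcal, the unweighted mean of the ten American baseline mains in Appendix A ("Below is the example of this for the American C/CL condition"): 0.02 × 973 = 19.46 kcal.

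**Formulas**, with b = level-2 and w = level-1 variance:
- SE(main) = √[(b + w/6) × 4/1000]
- SE(education interaction) = SE(main) × √(1/0.4 + 1/0.6) = SE(main) × 2.041
- SE(familiarity interaction) = √[w × (1/3 + 1/3) × 4/1000], in which b cancels
- Power = Φ(d/SE − 1.96) + Φ(−d/SE − 1.96)

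**Plan's own variances.** With b = w = 47,244, the total is 94,488 (SD 307), the ICC is 47,244/94,488 = 0.50, and b + w/6 = 55,118.

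| Test | SE (kcal) | Printed power | Power at 14.12 kcal | Power at 19.46 kcal | Effect giving printed power |
|---|---|---|---|---|---|
| Main effect | 14.85 | 0.93 | 0.16 | 0.26 | 51 kcal (7.2% of 706) |
| Education interaction | 30.31 | 0.81 | 0.08 | 0.10 | 86 kcal (12.2%) |
| Familiarity interaction | 11.22 | 0.86 | 0.24 | 0.41 | 34 kcal (4.8%) |

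The printed powers are not reproduced. One-sided testing at 14.12 kcal gives only 0.24 / 0.12 / 0.35.

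**Varying the unsupported input.** The total variances are 47,224 (the earlier figure read as a total), 86,661 (uniform random choice from the Appendix A menu, SD 294) and 94,488 (the plan's total). The ICC values are assumptions. Cells show main / education / familiarity power.

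| Total variance | ICC | At 14.12 kcal | At 19.46 kcal |
|---|---|---|---|
| 47,224 | 0.1 | 0.54 / 0.17 / 0.26 | 0.81 / 0.28 / 0.45 |
| 47,224 | 0.5 | 0.27 / 0.10 / 0.43 | 0.46 / 0.15 / 0.69 |
| 86,661 | 0.1 | 0.33 / 0.12 / 0.16 | 0.55 / 0.18 / 0.27 |
| 86,661 | 0.5 | 0.17 / 0.08 / 0.26 | 0.28 / 0.10 / 0.44 |
| 94,488 | 0.1 | 0.31 / 0.11 / 0.16 | 0.52 / 0.17 / 0.25 |
| 94,488 | 0.5 | 0.16 / 0.08 / 0.24 | 0.26 / 0.10 / 0.41 |

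At a fixed total, raising the ICC lowers the first two powers and raises the third.

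**Check that does not need the variance.** Power 0.93 requires d/SE = 1.96 + 1.476 = 3.436. For an equal effect the education interaction then has d/SE = 3.436/2.041 = 1.683, and power Φ(1.683 − 1.96) = 0.39. No choice of b and w gives 0.93 and 0.81 together at the same kcal effect.

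**The case against.** The strongest reply is that using one figure at both levels may be cautious. If 47,224 was the variance of a single order, doubling it overstates the noise and the tests are better than modelled. The earlier trial's data are not in the documents, so this cannot be excluded. That stands, and it is why the input should be called unsupported and not invalid.

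The Appendix A menu also does not show the plan's total to be wrong. Uniform choice from one of six menus is neither an observed distribution nor an upper bound, and SD 294 is close to SD 307.

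A reader might infer that choices across six unlike cuisines correlate below 0.5, so that the familiarity power is overstated and slips by some amount from 0.86. The documents do not support this. They give no ICC, and at the plan's variances 0.86 belongs to an effect of about 34 kcal, not to 2%. A loss measured from 0.86 has no baseline in the plan.

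The claim that familiarity precision depends only on level 1 assumes a random intercept and constant level-1 variance. Section 7.4 mentions an unstructured covariance, which might not reduce to that. The two-level model in Section 7.6 does fit that description, so the check follows the plan's own power model.

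Finally, the design is not shown to be too small for the effect the plan expects. At 7% of 706 (49.4 kcal), main-effect power under the plan's variances is about 0.91. The criticism is of the powers quoted for 2%.

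**Conclusion.** The concern holds as a lack of support. The within-participant variance and the ICC of 0.50 have no source, and the direction of any error cannot be told from the documents.

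The three printed powers are not supported at the stated 2%. Over the totals and ICCs tried (0.1 to 0.5):
- main-effect power is about 0.16 to 0.54 at 14.1 kcal, or 0.26 to 0.81 at 19.5 kcal;
- education-interaction power is about 0.08 to 0.17, or 0.10 to 0.28;
- familiarity-interaction power is about 0.16 to 0.43, or 0.25 to 0.69.

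These ranges rest on the two assumed reference means, two-sided testing, the 40/60 education split and the random-intercept model. Replacing the variance alone will not restore the printed figures, because the reference mean and effect size also need to be stated. This is a matter of planning and reporting. It does not bias the analysis.

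**What to change.** In Section 7.6:
1. State the mean to which the 2% applies.
2. Give a sourced value for each variance component of main-dish energy, from the main-item data of the earlier trial or from the trial's own menus with a stated choice assumption.
3. Rerun MLPowSim at N = 1,000 over an ICC range such as 0.1 to 0.5, and report its settings.
4. Restate the three powers as ranges. Alternatively, keep the quoted powers and state the effects they correspond to, about 51 / 86 / 34 kcal under the plan's present variances.

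N stays as it is. The cost is one rerun of the simulation and revised wording. The downside is less favourable stated powers, most plainly for the education interactions.

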## 2. OBJECTIVES, OUTCOMES MEASURES AND HYPOTHESES

OBJECTIVES	OUTCOME MEASURES	HYPOTHESES
Primary objective  To examine the effect that an information-based intervention (energy labelling)	Energy (kcal) of the ordered meal.	An increased availability of lower energy menu options will result in a decrease in total

and a structural intervention (increased availability of lower kcals options) have on kcals ordered in a hypothetical meal ordering task among participants of lower and higher SES.
		
energy ordered among both participants of lower and higher SES. However, energy labelling may exert a stronger effect on energy ordered among participants of higher vs. lower SES.

Secondary objectives
 
To examine the reasons why the effects that energy labelling have on kcals ordered may vary based on a participants' SES.
 
To examine the effect of labelling on familiar and unfamiliar cuisines menus.
	
Health motivation in food choices (questionnaire score).
 
Energy (kcal) of the ordered meals for familiar and unfamiliar cuisines.
	
The participants of higher SES will be more motivated by health in their food choices than participants of lower SES, which will mediate the relationship between SES and the effect of energy labelling on the total energy ordered.
 
Energy labelling will have a greater effect for unfamiliar compared to familiar cuisines.

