### 4. PARTICIPANTS AND RECRUITMENT

#### 4.1. Recruitment

Participants will be recruited through an online recruitment panel (Prolific) in which participants are compensated proportionate to the time it takes to complete the online study ( $\approx \$6$ /hour reward participants). Participants' recruitment will be stratified by gender (50% male, 50% female), student status (8% yes and 92% no) [24] and highest achieved education level (10% less than high school, 30% high school completion, 30% some college or associate's degree, 20% bachelor's degree, 10% advanced degree) to be representative of US adults [25].

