#### Menus

The design of the restaurant menus will be based on menus from existing US restaurants. In a recent study, 1,184 American adults were asked which of 34 national cuisines they had tried and whether

they liked or disliked them [26]; results are summarised in **Appendix B**. Based on these results we selected three familiar (tried by at least 90% of US people: American, Mexican and Italian cuisines) and three unfamiliar cuisines (never tried by approximately 50% of US people: Lebanese, Peruvian, Moroccan cuisines) for American people. Using the online menus of US restaurants offering the selected cuisines, we will then create sample menus for the six distinct restaurant cuisines, each consisting of 10 main dishes and a selection of between 5 sides and 5 desserts (including actual food names, description and prices).

For familiar cuisines, the menu-model restaurants will be US popular chain restaurants (>800 outlets across the country); for unfamiliar cuisines, they will be US restaurants offering these specific types of cuisines that will be chosen by searching for restaurants in large US cities: New-York, Los Angeles, Chicago, Houston (using Yelp, Tripadvisor). All the food items (and their description) included in the experimental menus will be based on existing US restaurants. Because kcal labelling is only mandatory for restaurant chains in the US, we will use external sources to calculate the energy content per 100g of the menu options available for unfamiliar cuisines (e.g., online recipes, national food composition databases). All the six menus will offer a similar range of main options in terms of energy content (i.e., similar min, median and max).

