If the above analyses reveals a significant interaction between *labelling* or *availability* condition and *highest educational qualification* on *energy of the main*, analysis will be stratified by *highest educational qualification (lower vs. higher)* and two linear mixed models will be fitted to examine the effect of *labelling* and *availability* on *energy of the main* for lower and higher educational qualifications.

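### The powers stated for 2% effects (0.93, 0.81, 0.86) do not follow from the plan's own sample size and variances; the education interaction has power of about 0.08 to 0.15, not 0.81

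*Combined protocol and SAP*

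**What the plan says.** Section 7.6 assumes 1,000 analysed participants, six orders each, a variance of 47,244 at both the order level and the participant level, and alpha 0.05. It cites MLPowSim and gives three powers:

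- main effects: "allows to detect 2% energy reduction and above at power = 0.93 due to labelling and/or availability";
- education interaction: "an additional 2% energy reduction (or above) in participants of higher educational qualification at power = 0.81";
- familiarity interaction: "an additional 2% energy reduction (or above) for unfamiliar menus at power = 0.86".

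No base is named for the 2%. The only overall mean in the section comes from earlier restaurant trials: "The weighted average kcal ordered in the no label condition was 706 kcal". The effect expected from that literature is 47 kcal, or 7%.

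The education contrast belongs to the primary objective in Section 2, where "energy labelling may exert a stronger effect on energy ordered among participants of higher vs. lower SES". Section 7.4 makes the education-stratified models conditional on that result ("If the above analyses reveals a significant interaction between" a condition and education), and Section 7.5 does the same for the moderated mediation analysis.

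**The concern.** The three powers are close together although the three contrasts have very different precision. A condition-by-education contrast divides each condition into two unequal subgroups of participants, so its standard error is about twice that of the main effect. A condition-by-familiarity contrast is made within participants, so the participant variance cancels and it is the most precise of the three. Equal 2% effects should therefore give widely separated powers. A 2% effect is also small against a standard deviation of about 217 kcal.

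At stake is how a null education interaction will be read. Someone relying on 0.81 would take non-significance as fair evidence that labelling works equally well in both education groups. The same test also decides whether the stratified and mediation analyses take place.

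**Working it through.** **Inputs**

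- N = 1,000, six orders, V1 = V2 = 47,244, alpha 0.05: Section 7.6. Two-sided testing is my assumption; the plan does not say.
- Equal allocation to four conditions (Section 6), so 500 against 500 for either factor.
- Three familiar and three unfamiliar menus: Section 3.
- Education: Section 4.1 recruits "10% less than high school, 30% high school completion", and Section 7.2 codes these two levels as lower. That gives 40% lower and 60% higher, or 200 and 300 per level of a factor.

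**Standard errors (random-intercept model)**

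Variance of a participant's mean over six orders: 47,244 + 47,244/6 = 55,118.

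- Main effect: √(55,118 × 2/500) = 14.85 kcal
- Condition × education: √(55,118 × (2/200 + 2/300)) = 30.31 kcal
- Condition × familiarity: √(47,244 × (1/3 + 1/3) × 2/500) = 11.22 kcal

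**Power for a 2% effect**

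With δ = 0.02 × base, power = Φ(δ/SE − 1.96) + Φ(−δ/SE − 1.96). For example, the education interaction on 706 kcal has δ = 14.12 and δ/SE = 14.12/30.31 = 0.466, so power = 0.075.

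| Base (kcal) | 2% (kcal) | Main | Education | Familiarity |
|---|---|---|---|---|
| Stated in plan | – | 0.93 | 0.81 | 0.86 |
| 706 (Section 7.6) | 14.1 | 0.16 | 0.08 | 0.24 |
| 973 (mean of American control menu, Appendix A: 9,730/10) | 19.5 | 0.26 | 0.10 | 0.41 |
| 1,360 (highest main on that menu) | 27.2 | 0.45 | 0.15 | 0.68 |

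Simulation from the same inputs (4,000 runs per cell) gave 0.161, 0.070 and 0.240 on 706 kcal, and 0.452, 0.151 and 0.690 on 1,360 kcal. None of the plan's three figures is reproduced.

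**Working backwards**

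The effect with the stated power is (1.96 + z) × SE, where z is the normal quantile of that power:

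- 0.93, main: 51.0 kcal, which is 2% of 2,551 kcal
- 0.81, education: 86.0 kcal, which is 2% of 4,301 kcal
- 0.86, familiarity: 34.1 kcal, which is 2% of 1,706 kcal

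All three bases exceed the highest main on the example menu, and Section 5.1 says "All the six menus will offer a similar range of main options in terms of energy content". They also disagree with each other, so naming a base cannot repair the set. A 51 kcal effect has power 0.93 as a main effect but 0.39 as an education interaction.

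**Reading 'and/or' as at least one of the two factors**

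With independent tests and both effects present, power is 1 − (1 − p)²:

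| Base (kcal) | Main | Education | Familiarity |
|---|---|---|---|
| 706 | 0.29 | 0.14 | 0.43 |
| 973 | 0.45 | 0.19 | 0.65 |
| 1,360 | 0.70 | 0.27 | 0.90 |

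The bases needed become 1,922, 3,215 and 1,280 kcal. Only the familiarity figure comes within the menu range.

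**Education split**

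On 706 kcal the education power is 0.072 to 0.076 for lower-education shares of 30% to 50%, so the split hardly matters.

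**Effects of the size the plan cites**

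| Effect | Main | Education |
|---|---|---|
| 47 kcal | 0.89 | 0.34 |
| 7% of 706 = 49.4 kcal | 0.91 | 0.37 |

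**The case against.** The plan does not state sidedness, and its hypotheses are directional. One-sided powers are higher: 0.24, 0.12 and 0.35 on 706 kcal, and 0.57, 0.23 and 0.78 on 1,360 kcal. Adding the at-least-one-factor reading on 1,360 kcal gives 0.82, 0.40 and 0.95. So 0.27 is the ceiling for education only under two-sided testing. With both concessions it is 0.40, still half the stated 0.81.

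The 706 kcal base comes from purchases on other menus, while the outcome here is the energy of the main. The 973 kcal base is nearer to this study. That is fair, but it moves the education power only from 0.08 to 0.10. The 1,360 kcal maximum rests on one example menu, and the others are promised to be similar, not identical. A somewhat higher maximum is possible, but not one near 4,301 kcal.

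The MLPowSim inputs are not reported, so the run may have used something else. What can be said is that the powers do not follow from the stated inputs. Setting the participant variance to zero, against the plan's own text, still gives the education interaction only 0.23 on 706 kcal and 0.66 on 1,360 kcal. A wider search over coding, sample size, variance splits and sidedness found no combination with N = 1,000 and a base up to 1,360 kcal that came within 0.07 of all three figures.

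Finally, neither the sample size nor the analysis changes, and the plan does not claim to expect a 2% education difference. That limits the consequence to what readers are told about power, but on that point the statement is wrong by a wide margin for part of the primary hypothesis.

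**Conclusion.** The concern holds and must be fixed. From the plan's own inputs, a 2% education interaction has power of about 0.08 (706 kcal) to 0.15 (1,360 kcal), against 0.81 stated. The main-effect figure is 0.16 to 0.45 against 0.93, and the familiarity figure 0.24 to 0.68 against 0.86. No single base yields all three. This rests on a random-intercept model with the stated variances, two-sided 5% tests of each factor separately, and the 40/60 education split; none of the alternatives above brings the education figure to 0.81.

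The sample of 1,000 is not in question for main effects of labelling or availability of the size the plan expects.

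**What to change.** Keep 1,000 participants and rewrite the power statement in Section 7.6:

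- Give the effects detectable at 80% power, (1.96 + 0.84) × SE: about 42 kcal (main effect), 85 kcal (education interaction) and 31 kcal (familiarity interaction).
- Name the base for any percentage. On 706 kcal these are 5.9%, 12.0% and 4.5%.
- State whether tests are one- or two-sided, and whether 'and/or' means each factor or at least one.
- State power of about 0.89 for the cited 47 kcal labelling effect and about 0.34 for an education difference of that size.
- Say that a non-significant education interaction will not be taken as evidence of equal effects.
- If the MLPowSim run used other inputs, report them.

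Optionally, state the weights behind the 706 kcal mean. The footnote values give 732 weighted by n, 712 by inverse variance and 705 unweighted; the effect on power is trivial.

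The cost is rewording of one section, with no extra participants and no change to the analysis. The stated powers become less favourable, above all for the education interaction.
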